1. OBJECTIVES

1.1 Primary objective of Lead In

- To evaluate the safety, tolerability and feasibility of M7824 when administered together with SBRT reirradiation.

1.2 Primary objective of Phase 2

- To evaluate the progression-free survival (PFS) rate of M7824 plus SBRT reirradiation at 1 year

1.3 Secondary objectives

- To evaluate the overall response rate by RECIST or RECIST 1:1
- To evaluate the 1- year locoregional control (LRC), locoregional failure-free survival (LFFS), distant metastasis (DM) and overall survival (OS) rates
- To evaluate acute and late toxicity using Common Terminology Criteria for Adverse Events (CTCAE)-v5.0
- To evaluate fibrosis-related toxicities and functional outcomes
- To evaluate Patient Reported Outcome (PRO) measures of symptoms using MD Anderson Symptom Inventory (MDASI).
- To evaluate volumetric tumor regression rate and MRI kinetic biomarkers after M7824 plus SBRT
- To compare Quality-Adjusted-Life-Years (QALY) between M7824 plus SBRT reirradiation and historic SBRT reirradiation control

1.4 Exploratory Objectives

Biomarkers will be accessed in the tumor and blood samples and correlated with clinical outcomes and toxicity. Correlative tissue studies include but are not limited to profiling of the tumor immune microenvironment by IHC and multiplex immunofluorescence analyses (mIF) including quantitative assessment of CD8 T cells and PD-L1 expression levels, immune gene expression signatures by NanoString or HTG, target DNA sequencing to access tumor mutational burden, detailed assessments of immunocyte populations and functional markers by multicolor flow cytometry, and other biomarkers that may emerge to be important related to the use of the proposed agent. Blood will be collected prior to cycles 1, 3 and at disease progression (3 time points) for evaluation of ctDNA, circulating immune biomarkers of interest including cytokines, and measurements of T-cell activation by flow cytometry. Functional outcome measures include but are not limited to validated clinical grading criteria (Head and Neck-Lymphedema and Fibrosis, HN-LEF)^{1,2} and patient-reported measures of head and neck fibrosis (Lymphedema Symptom Inventory Distress Scale, L-SIDS)³, as well as radiographic dysphagia grade (Dynamic Imaging Grade of Swallowing Toxicity, DIGEST)⁴, and cervical range of motion (CROM). Correlative imaging studies include functional and anatomic magnetic resonance imaging (MRI).

2. BACKGROUND AND RATIONALE

Stereotactic Body Radiation Therapy (SBRT) enables precise and focused delivery of ablative dose radiation in a few fractions and is capable of providing durable local-regional control in patients with recurrent head and neck squamous cell carcinoma (HNSCC)^{5,6}, after a median follow-up of 16.7 months,

the 1-year disease control within the reirradiation field (hereafter referred to as local control) is 84% among 67 patients with recurrent HNSCC treated with SBRT reirradiation at MD Anderson. Although the local control with SBRT reirradiation is promising, recurrences outside the reirradiation field remains problematic, with 1-year regional and distant recurrence rates of 18.2% and 21.2%, respectively. Furthermore, while head and neck reirradiation provides high local control rates, it is associated with severe, long-term treatment related adverse events such as fibrosis and dysphagia, with rates as high as 40%^{7,8}. Even with the use of conformal radiotherapy techniques such as intensity modulated radiation therapy (IMRT) or proton therapy, the 2- year rates of \geq grade 3 toxicity approach 30%^{9,10}.

Transforming growth factor beta (TGF β) is a cytokine frequently overexpressed by cancers that promotes epithelial-to-mesenchymal transition and is immune suppressive in the tumor microenvironment. TGF β suppresses the expression of IFN γ and induces differentiation of immune suppressive Tregs. Notably, co-targeting of TGF β and immune checkpoints PD-1/L1 or CTLA4 demonstrates greater tumor control than either alone in *in vivo* models of melanoma¹¹. M7824 is a first-in-class bi-functional fusion protein composed of a monoclonal antibody (mAb) against programmed death ligand 1 (PD-L1) fused to a TGF β “trap”. M7824 was well tolerated in patients with heavily pretreated solid tumors and promising clinical activity was seen particularly in HPV-related cancers. In addition to the therapeutic effects of blocking PD-L1, the TGF- β trapping property of M7824 has potential for anti-inflammatory and anti-fibrosis activity^{12,13}.

In spite of a recent small randomized trial of nivolumab with SBRT versus nivolumab alone in 53 recurrent HNSCC patients not showing an improvement in overall response rate, progression-free and overall survival over nivolumab alone¹⁴, abscopal response in patients with widely metastatic HNSCC has been reported¹⁵. Furthermore, trials of radiotherapy and immune checkpoint blockade have demonstrated abscopal response in non-irradiated lesions between 10 and 27% of patients with metastatic melanoma^{16,17}. Anti-PD1 can also potentiate the radiation effect locally, which is particularly attractive in the proposed population with oligo, loco-regional recurrent disease amenable to radio-ablative re-irradiation, and pre-clinical studies using mouse models demonstrated significantly less radiation-induced inflammation and fibrosis by the concurrent administration of TGF- β inhibitors^{18,19}.

In summary, rationale for evaluating the combination of SBRT and M7824 in patients with recurrent, previously irradiated HNSCC include: (1) the increasing evidence for radiotherapy to generate antitumor immune response and synergize with PD-L1 inhibitors; (2) the compelling preliminary efficacy and safety data of M7824 in patients with refractory solid tumors; (3) the synergy between co-targeting of PD-1/L1 and TGF β in the tumor microenvironment; and (4) the anti-fibrotic properties of M7824 due to its anti-TGF- β component to mitigate reirradiation fibrosis/toxicity. These findings support a strong rationale for testing M7824 in combination with SBRT in patients with local-regionally recurrent, previously irradiated HNSCC.

2.1 Introduction

HNSCC account for over 550,000 cases worldwide and 55,000 cases in the U.S. annually, with an estimated 12,000 dying each year from the disease²⁰. Radiotherapy, alone or in combination with chemotherapy, is integral to the treatment of many HNSCC, either in the primary management as part of an organ preservation approach or in the adjuvant setting after surgery²¹. Despite improvements in

HNSCC treatment, local-regional recurrence occurs in 15-50% of patients and is the most common cause of death²²⁻²⁴. Among survivors, secondary primary HN tumors can occur in up to 40% of patients²⁵.

Although, salvage surgery is historically the treatment of choice among patients with recurrent or second primary HNSCC after radiotherapy, many have unresectable disease, are medically unfit, or refuse surgery for various reasons, including loss of organ function^{26,27}. In these patients, the previous standard-of-care was chemotherapy. Unfortunately, the prognosis with chemotherapy alone is poor, with pooled-analyses showing a median survival of 7.4 months compared to 4.6 months with supportive care alone, with a marginal improvement to 10 months with the addition of cetuximab to platinum-based chemotherapy^{24,28 26,29}. Furthermore, prior radiation has been reported as an independently poor prognostic factor in patients receiving systemic therapy for recurrent HNSCC³⁰.

2.2 Reirradiation

In select patients who are not surgical candidates, reirradiation is a potentially curative treatment option^{3,4}. However, head and neck reirradiation is a clinical challenge, and carries a significant risk of severe morbidity and toxicity to nearby normal tissue⁵. Reirradiation with older two-dimensional (2D) and three-dimensional (3D) approaches have yielded modest local-regional control (LRC) rates of up to 50% at 3 years, albeit with serious treatment-related toxicity risks, including 40-60% grade 3 or higher toxicity and up to 20% treatment related deaths^{6,9 27,31}. An additional challenge with recurrent HNSCC is the development of tumor radioresistant clones acquired through prior treatment, which may limit the effectiveness of subsequent therapy^{26,32}. Proposed retreatment strategies to reduce reirradiation toxicity and overcome tumor radioresistance include the use of conformal radiotherapy techniques, altered fractionation strategies and/or the addition of systemic radiosensitizers. More-recently, the combination of immunotherapy and radiotherapy has demonstrated synergy³³.

2.3 Stereotactic Radiotherapy

Modern highly conformal radiotherapy techniques, such as intensity modulated radiation therapy (IMRT), proton therapy, and SBRT are attractive options for those with recurrent HNSCC. Retrospective and prospective reports have demonstrated improved local disease control and survival compared with use of 2D and 3D radiotherapy³⁴⁻³⁶. Our institution recently published the largest series of 207 patients reirradiated with IMRT with curative intent. The 2-year LRC and overall survival (OS) rates were 65% and 57%, and 5-year rates were 49% and 42%, respectively⁹. The median survival was 25.1 months overall and 22.5 months for patients with SCC histology. The grade 3 or higher treatment related morbidity was 32% at 2 years and 48% at 5 years. Multivariate analysis showed that retreatment volume >50 cc (P=0.001) and use of platinum based chemotherapy (P=0.02) were associated with higher late grade 3 toxicity rates⁹. Similarly, our recently published study of 60 patients reirradiated with proton beam showed 2 year LRC and OS rates of 73% and 70%, respectively. The 2 year late grade 3 or higher toxicity rate was 26%¹⁰.

SBRT enables precise and focused delivery of ablative dose radiation in a limited number of treatments (typically 1-5) and has become a standard approach in several disease sites such as lungs, brain and prostate³⁷⁻⁴¹. Logistical and financial advantages of SBRT over existing conformal radiotherapy modalities include fewer number of treatments, shorter treatment duration (typically <2 weeks vs 6-7

weeks), fewer clinic visits and/or lost work hours. Clinical advantages of SBRT include reduced exposure of nearby normal tissues to reirradiation dose, use of ablative/high doses to confer additional mechanisms of cell kill, superior immune elicitation compared with standard fractionation, and a shorter interval to systemic therapy that benefits a population at high risk for metastatic development⁴².

A growing body of literature demonstrates SBRT for HNSCC reirradiation can provide durable local-regional control and is well tolerated relative to conventionally fractionated RT^{37-41 29-30}. Retrospective and prospective studies from the University of Pittsburgh and others demonstrate SBRT is associated with late grade 3 toxicity rates between 10% and 30% when delivered with every other day (QOD) frequency. The 2-year local control rates were 35-65% and 1-year OS rates were 30-60%^{43,44 41,45,46}. Our recently reviewed institutional experience of 101 patients with recurrent HNSCC reirradiated with SBRT to a median dose of 45 Gy in 5 fractions (delivered QOD) showed a 1-year local control rate of 87%, with a median follow-up of 15.9 months (unpublished data). Patient reported quality of life outcomes showed lower symptom burden associated with SBRT⁴⁷. No difference in disease control rate or progression free survival for recurrent versus second primary tumors in a previously radiated field was noted on our institutional data, which is consistent with other published experiences^{9,48,49}.

Although local control with SBRT reirradiation is promising, recurrences outside the reirradiation field remains problematic. Our data demonstrates 1- and 2- year regional recurrence rates of 16% and 24%, respectively, and 1- and 2-year distant recurrence rates of 16% and 28%, respectively (manuscript in progress). Furthermore, head and neck reirradiation is associated with severe, long-term treatment related adverse events, with rates of severe fibrosis/dysphagia as high as 40%^{7,8}. Even with the use of conformal IMRT and proton radiotherapy, 2-year grade 3 or higher toxicity rates approaches 30%^{9,10}.

2.4 Checkpoint Inhibitors in Head and Neck Cancer

Cancer immunotherapy is based on the premise tumors can be recognized as foreign invaders and effectively killed by an activated immune system. However, it is also recognized that tumor-infiltrating lymphocytes (TILs) in proliferating cancers can be rendered ineffective by the tumor microenvironment. The pathogenesis and progression of HNSCC may therefore be facilitated by local immunosuppressive alterations. Down-regulation of T cell function has been reported in HNSCC. And is thought to be mediated by multiple mechanisms. These include increased expression of the programmed death receptor ligand-1 (PD-L1) in tumor cells, suppression of TIL activity by tumor associated fibroblasts, production of immune suppression factors such as TGF-β, and co-stimulation of B7-CD28 family molecules^{50 51,52}. Recurrent HNSCC can be particularly immunosuppressive, with impaired natural killer (NK) activity, reduced antigen-presenting function, impairment of tumor infiltrate lymphocytes (TILs), and increased population of suppressive Treg^{51,53-56}.

PD-L1 is one of two specific ligands for the programmed death receptor-1 (PD-1), a transmembrane protein and a member of the CD28 family of T-cell co-stimulatory receptor expressed on activated T cells. PD-L1 has been shown to down-regulate T-cell activation upon binding to PD-1. PD-L1 expression on tumor cells has been correlated with increased tumor aggressiveness, development of distant metastasis and decrease survival⁵⁷. Several clinical trials of anti-PD-L1 therapy have demonstrated clinical activity of immunotherapy in patients with heavily pre-treated, recurrent/metastatic HNSCC. Several clinical

trials (Keynote 12; Keynote 55) have demonstrated an ORR of 11-22% and 1 year OS of 38% (Keynote 12) with use of single agent anti-PD1 or anti-PD-L1 monoclonal in those with recurrent metastatic HNSCC. Importantly, data from a phase III trial (CheckMate 141) demonstrated that anti-PD-1 improved survival of patients with platinum-refractory recurrent or metastatic HNSCC compared to standard of care chemotherapy and reduced the risk of death by 30% (HR 0.70, 96% CI 0.51-0.96) compared to single agent methotrexate, docetaxel or cetuximab of investigator's choice¹². The 1-year OS was 36% with anti-PD-1.

More recently results of CheckMate-048 published in abstract form demonstrated that anti-PD1 as a single agent is non-inferior to chemotherapy with cetuximab in the first line setting and superior to chemotherapy with cetuximab in patients with a PD-L1 combined positive score of at least 1%, supporting anti-PD1 as a standard of care first line therapy for patients with recurrent/metastatic HNSCC⁵⁸.

TGF- β plays a critical role in regulation of epithelial proliferation and differentiation, and disruption of TGF- β signaling is common in HNSCC⁵⁹. TGF- β overexpression in the tumor microenvironment promotes tumor immune evasion and metastasis and is associated with poor prognosis. TGF- β is a critical mediator of epithelial-to-mesenchymal transition to promote immune evasion and metastasis of HNSCC. Moreover, TGF- β is immunosuppressive in the tumor microenvironment. It decreases activity of Anaphase-promoting complex (APC) and NK cells, decreases T cell proliferation, facilitates recruitment of Tregs, promotes M2 polarization of TAM and angiogenesis by increasing VEGF production by TAM. TGF- β also mediates cell cycle quiescence and resistance to chemotherapy in squamous cell carcinomas⁶⁰. TGF- β is also implicated as a driver of numerous fibrotic diseases through stimulation of collagen deposition, including the fibrosis induced by radiotherapy⁶¹. As a consequence of its pathophysiological roles in cancer and fibrotic syndromes, numerous TGF- β inhibitors have been developed⁶².

2.5 M7824: Rationale For Combination PD-L1 and TGF- β -inhibition

M7824 is a first-in-class bifunctional fusion protein composed of a mAb against PD-L1 fused to a TGF β "trap". M7824 consists of the PD-L1 antibody linked to the extracellular domain of 2 TGFBRII molecules⁶³. Synergy between TGF β inhibition and anti-PD-L1 has been demonstrated in animal models, supporting the combination into one molecule¹¹. M7824 blocks the immunosuppressive effects of TGF β on NK cell function⁶³. M7824 has also been shown to reverse EMT, a mechanism of immune evasion, in lung cancer⁶⁴. M7824 also demonstrated synergy with radiotherapy and enhanced the abscopal effect. In phase 1 clinical trials, the maximal tolerated dose could not be defined with the highest dose level tested being 20mg/kg every 2 week¹³s. Based upon pharmacokinetic data, a dose of 1200 mgs every 2 weeks has been chosen for further development.

In a phase I 3+3 dose escalation and expansion study of 19 patients, M7824 was well tolerated in patients with heavily pretreated solid tumors and promising clinical activity was seen. Responses observed include a complete response in a patient with cervical cancer, 2 partial responses in anal and pancreatic cancer, and prolonged stable disease in 6 subjects¹³.

Based upon a total of 377 patients in expansion cohorts, M7824 administration has been associated with infusion-related reactions, immune mediated adverse events and skin lesions with hyperkeratosis, which is a known drug class effect of TGF- β inhibitors. The most frequent treatment related adverse events of any grade were pruritus (11.4%), rash (13%), diarrhea (9%), asthenia (10.3%), fatigue (7.7%), decreased

appetite (5.6%) and anemia (6.1%). Of the 377, 58 subjects (15.4%) experienced at least 1 grade 3 or greater adverse event. These included anemia, rash, colitis, diarrhea, vomiting, lipase increase, ALT increase, fatigue, acute kidney injury, hypophosphatemia and keratoacanthoma (0.5%). One subject with pancreatic cancer had a grade 4 lipase increase and 1 subject died from grade 5 hemolysis, thrombocytopenia and dyspnea.

Additional details regarding the clinical development of M7824 as well as adverse events are provided in the attached Investigator's Brochure.

2.6 M7824 and SBRT

Recurrences outside the reirradiation field remain problematic. Furthermore, while head and neck reirradiation offers the promise of durable disease control, it is associated with severe, long-term treatment related fibrosis and dysphagia^{7,8}.

The combination of targeted SBRT and immune checkpoint inhibition offers the potential to control the local recurrence using smaller reirradiation fields while mitigating disease recurrence regionally and distantly. Studies have shown their combination have been improved antitumor activity compared to either therapy alone¹⁶. Recent trials of radiotherapy and immune checkpoint blockade demonstrate abscopal response in unirradiated lesions in 10-27% of patients with metastatic melanoma¹⁷. In addition to blocking PD-L1, M7824 TGF-β trapping properties have anti-inflammatory and anti-fibrosis activity¹². Pre-clinical studies using mouse models demonstrated significantly less radiation-induced inflammation and fibrosis when concurrent administered with TGF-β inhibitors^{18,19}.

Therefore, there is a strong impetus to evaluate the combination of SBRT and M7824 in patients with recurrent, previously radiated HNSCC based on the following rationale: (1) evidence for radiotherapy to generate antitumor immune response and synergize with PD-L1 inhibitors; (2) compelling preliminary efficacy and safety data of M7824 in patients with refractory solid tumors; and (3) M7824 anti-fibrotic properties from its anti-TGF-β component.

2.7 Functional and patient reported outcome measures

An unanswered question is how specific immune checkpoint blockade and radiotherapy toxicities can impact health-related quality of life (HR-QOL) and function. A few studies have suggested that HR-QOL scales, together with clinical data, might improve survival prediction^{65-67 19,20,21}. While PRO and quality of life and symptom burden measures of this population are of great interest, there are few prospective studies that assess the impact of SBRT and checkpoint inhibitor blockade. In this setting, an additional purpose of this study is to analyze functional and patient reported outcome measures with the combination of M7824 plus SBRT reirradiation for recurrent HNSCC. To minimize survey burden and personalize PROs to expected patterns of toxicity, the PRO bundle differs by site of recurrence (mucosal, neck, skull base anterior v non-anterior) as detailed in Table 1.

3. PATIENT ELIGIBILITY

3.1 Inclusion Criteria

Patients with histologically documented local-regional recurrent squamous cell carcinoma of the head and neck, or second primary squamous cell carcinoma of the head and neck;

Patients must be willing to undergo research biopsy for tissue collection at baseline and at disease progression;

Previous receipt of at least 30 Gy of radiation for HNSCC with overlapping fields;

Not eligible or poor candidate or patient refusal of surgery for recurrence;

Evaluable disease apparent on imaging (MRI or CT);

1 to 3 sites of recurrence (<60 cm³ per site, total volume <100 cm³);

Age ≥ 18 years;

Eastern Cooperative Oncology Group (ECOG) = 0, 1, or 2;

Adequate hematologic function defined as follows:

WBC ≥ 2000/µL;

Absolute neutrophil count (ANC) ≥ 1,500 cells/mm³;

Platelets ≥ 100,000 cells/mm³;

Hemoglobin ≥ 9.0 g/dl; Note: The use of transfusion or other intervention to achieve Hgb ≥ 9.0 g/dl is acceptable.

Adequate renal function as follows:

Serum creatinine ≤ 1.5 mg/dl or creatinine clearance (CC) ≥ 50 ml/min determined by 24-hour collection or estimated by Cockcroft-Gault formula:

$$\text{CCr male} = \frac{[(140 - \text{age}) \times (\text{wt in kg})]}{[(\text{Serum Cr mg/dl}) \times (72)]}$$

$$\text{CCr female} = 0.85 \times (\text{CrCl male}).$$

Adequate hepatic function as follows:

Total bilirubin ≤ 1.5 x ULN (except patients with Gilbert Syndrome who can have total bilirubin < 3.0 mg/dL);

AST or ALT ≤ 3 x the upper limit of normal.

Negative serum pregnancy test for women of childbearing potential and confirmation within 24 hours of first dose of study drug.

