3.2 Exclusion Criteria

Presence of distant metastases;

Less than six-month disease free interval from end of prior radiotherapy to the head and neck;

Prior receipt of anti-PD-1/L1 therapy.

Patients who are pregnant or breast feeding;

Clinically significant uncontrolled major cardiac, respiratory, renal, hepatic, gastrointestinal or hematologic disease but not limited to:

Symptomatic congestive heart failure, unstable angina, or cardiac dysrhythmia not controlled by pacer device; myocardial infarction within 3 months of registration.

[figure not shown]
Active autoimmune disorder or immunosuppression (including HIV, but excluding endocrine abnormalities that are controlled with replacement medications);

Active viral hepatitis;

Steroid therapy of greater than prednisone 10 mgs a day or equivalent;

Prior history of invasive non-head and neck cancer within two years, with the exception of screen detected prostate cancer treated with observation only, basal cell and squamous cell carcinoma of the skin, and micro-invasive resected cervical carcinoma.

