5. STUDY EVALUATIONS

Table 1 summarizes the pretreatment (initial screening, baseline measures prior to enrollment), on treatment, post-treatment phases of the trial, and the evaluations that would be required during these phases.

TABLE 1: Summary of Study Evaluations

Procedure	Screening	On-Treatment	First Follow-up	Follow-Up
	Day -28 to D1	C1-C12, D1,D15 (+/- 3 days), Q28D cycles	90 days after last dose of M7824 (+/- 14 days)	Q6 mo. Yr. 2-5 (+/- 28 days)

Informed consent	X			
Medical history	X			
Physical exam	X	X	X	X
Vital signs	X	X	X	X
Dermatological exam	X	Every 3 mo.	X	X
Performance status	X	X	X	X
Review of prior radiation fields	X			
CT or MRI of neck	X	3, 6, 9, 12 mo.		18, 24 mo.
CT scan of chest ^d	X	3, 6, 9, 12 mo.		18, 24 mo.
BMP, creatinine, CBC diff, Mg, hepatic function	X	X	X	As clinically indicated
Lipase, amylase, TSH, free T4	X	X (every other cycle)	X	As clinically indicated
HBsAg, HCV Ab	X			As clinically indicated
Preg Test for childbearing women	X	Every 3 mo.		As clinically indicated
12 lead EKG	X			
Adverse event evaluation	X	X	X	
Tumor biopsy ^a	X			At progression
Blood (serum)for PK ^b		X		At progression

Blood (serum)for ADA ^b		X		At progression
Blood for biomarker analyses ^c		X	At progression	At progression
All patients				
Medical Photo	X			Q6 mo. Yr. 2-5
MDASI-HN	X	3, 6, 12 mo.		18, 24 mo.
EQ-5D	X	3 mo.		24 mo.
Radiation Swallow Pathway (all mucosal, all neck, non-anterior SB)				
Swallowing clinic/Therapy	X			
MBS	X	3-6 mo.		18-24 mo.
PSS-HN	X	3-6 mo.		18-24 mo.
CROM + HN-LEF	X	3-6 mo.		18-24 mo.
MDADI	X	3-6 mo.		18-24 mo
LSIDS-HN				
Mucosal primary only				
Video-Strobe +/-2 wks	X	3-6 mo.		18-24 mo.
Anterior skull base only				
ASBQ	X	3-6 mo.		18-24 mo

Footnote: Radiation Swallowing Therapy Pathway includes all patients with mucosal site of recurrent disease, all with cervical lymph node recurrence, and non-anterior skull base, MBS + MDADI, LSIDS-HN and CROM/HN-LEF occurs at baseline, 3-6 months and 18-24 months after end RT; assessment with SLP post-RT videostroboscopy and recommended on same schedule for mucosal primaries; SLP therapy visits are at clinician discretion but typically include a minimum of pre, during week 1, and end RT during week 2, and 6 weeks evaluation may include FEES particularly if laryngeal primary tumors.

- a. Mandatory tumor biopsies will be collected prior to treatment and at progression, refer to section 10.2 for details on tumor collection.

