13.5 Sample Size

The statistical considerations for the Phase I/II design are described as follows:

This is a phase I/II, open label, single arm study to evaluate M7824 plus SBRT in patients with locoregional recurrent HNSCC after prior head and neck radiotherapy that are not good candidates for salvage surgery (Figure 1). Patients must have evaluable disease by RECIST or RECIST 1:1 and a performance status ECOG 0-2. Time elapsed from prior radiotherapy must be at least 6 months.

Sample Size

In the phase I portion, 8 patients will be enrolled to access safety and toxicity. The primary endpoint is dose-limiting toxicity (DLT) defined as M7824 related \geq grade 3 adverse event (AE) unresolved to \leq grade 1 in \leq 28 days, or incomplete SBRT. DLT window is from first M7824 dose (D0) until 14 days post SBRT (D28). More than 2 DLTs in 8 evaluable patients will be considered unacceptable.

In the phase II portion, the primary endpoint is PFS at 1 year. Based on the prior studies [unpublished data from MD Anderson], we assume that the one-year PFS of the standard treatment is 0.60. If the new treatment improves the one-year PFS to 0.80 or higher, it will be considered a clinically important improvement. A sample size of 21 patients (with 1.5-year additional follow-up after the last patient is enrolled) will allow us to observe an improvement in 1-year PFS from 0.60 to 0.80. This will enable the study 80% power to detect the specified difference in PFS. Power was calculated using a log-rank test with a one-sided type 1 error rate of 0.10 (EAST 5.4 and STPLAN version 4.5). Based on our estimated accrual rate of 2 patients per month, we expect enrollment to be completed in 11 months. The total study duration is 29 months.

DMI (Data Management Initiative) database

Clinical data capture called DMI (Data Management Initiative) and CORe will be the electronic database used for this study's electronic case report forms.

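### The transaminase entry limit in section 3.1 is met when only one of AST and ALT is within 3 × ULN, and nothing else in the protocol puts a numeric limit on the other

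*Combined protocol and SAP*

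**What the plan says.** Section 3.1 defines adequate hepatic function in two lines. One concerns bilirubin: "Total bilirubin ≤ 1.5 x ULN (except patients with Gilbert Syndrome who can have total bilirubin < 3.0 mg/dL"). The other is the transaminase line: "AST or ALT ≤ 3 x the upper limit of normal". It does not say that both enzymes must be within the limit.

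The renal criterion just above it is also built on *or*: "Serum creatinine ≤ 1.5 mg/dl or creatinine clearance (CC) ≥ 50 ml/min determined by 24-hour collection or estimated by Cockcroft-Gault formula". There the word marks a true alternative, since meeting either limit is enough.

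Section 3.2 has two exclusions that bear on the liver: "Clinically significant uncontrolled major cardiac, respiratory, renal, hepatic, gastrointestinal or hematologic disease but not limited to", and "Active viral hepatitis". Table 1 in section 5 schedules "BMP, creatinine, CBC diff, Mg, hepatic function" at screening and on treatment, and hepatitis B and C serology at screening. It gives no enzyme threshold.

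Section 2.5 includes "lipase increase, ALT increase, fatigue, acute kidney injury" in its list of grade 3 or greater events among the 377 patients in the M7824 expansion cohorts. Section 10.2, under clinical laboratory assessments, asks for close monitoring of a clinically significant abnormal value that was not there at baseline.

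**The concern.** An inclusion criterion with an upper limit on two values, joined by *or*, is satisfied as soon as one value is low enough. Creatinine and creatinine clearance are two routes to the same quantity, so *or* works in the renal line. AST and ALT are separate laboratory values, and a limit on one does not limit the other.

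Two things are at stake. First, the hepatic entry safeguard can be passed with one enzyme above the stated limit, for a drug with grade 3 or greater ALT increase among its reported events. An enzyme already abnormal at entry also falls outside the wording of the close-monitoring instruction in section 10.2. Second, two screeners holding the same laboratory report can reach opposite decisions: one reads the line as the renal line reads, the other takes it to mean both enzymes.

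**Working it through.** The protocol states no figure to reproduce here, so the check is one of logic followed by a search of the text.

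**Step 1. The rule as a condition.** Let A be AST ≤ 3 × ULN and B be ALT ≤ 3 × ULN.

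| AST | ALT | A or B (as worded) | A and B (each enzyme) |
|---|---|---|---|
| within | within | met | met |
| within | above | met | not met |
| above | within | met | not met |
| above | above | not met | not met |

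The readings differ in exactly the two discordant rows. An illustrative patient with AST 2.9 × ULN and ALT 6 × ULN has A true and B false, so the line is met as worded and not met if each enzyme must comply. In the discordant rows this line places no upper bound on the second enzyme.

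**Step 2. Does usage within section 3.1 settle the reading?** The renal line uses *or* as a true alternative. The haematology requirements, all of which must hold, are listed as separate lines. Usage within the section therefore favours the literal reading of the transaminase line.

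**Step 3. Does other text cap the second enzyme?**
- Bilirubin limit, section 3.1: a different analyte.
- Uncontrolled major hepatic disease, section 3.2: a clinical judgement with no enzyme value.
- Active viral hepatitis, section 3.2: one cause, with no enzyme value.
- Screening laboratory panel, Table 1: hepatic function is measured, with no threshold.
- Section 10.2: relevant results must be checked before treatment is given, with no entry limit for AST or ALT.

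None of these sets a number for the second enzyme.

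**Step 4. Size.** The number of patients affected would be the number screened multiplied by the proportion with discordant enzymes who meet every other criterion. The documents do not give that proportion, so no count can be calculated. No sample-size, power or stopping-boundary calculation in section 13 uses this criterion.

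**The case against.** The best defence has three parts.

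*Passing one line is not eligibility.* A reader might infer that a patient with the second enzyme at any level can enroll. The documents do not support that. Bilirubin must also be within its limit, hepatitis serology is drawn at screening, and an investigator can exclude an extreme value as clinically significant uncontrolled hepatic disease. This part stands. What remains is that the last safeguard rests on judgement and that no number backs it up.

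*The sponsor probably meant both enzymes.* This is plausible, since the line can be read as one limit applying to either transaminase. But it supports the correction, because stating the intent would leave the intended population unchanged.

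*The safety consequences are modest.* This is largely right:
- Hepatic function is measured in everyone on treatment. Section 12 counts a worsening of a previous condition as an adverse event, so a rise from an abnormal baseline is not lost. A patient between 1 and 3 × ULN also enters with an abnormal value under either reading. The wording affects how abnormal the entry value may be, not whether it may be abnormal.
- A reader might infer that one misattributed enzyme event could reverse the lead-in decision, given "More than 2 DLTs in 8 evaluable patients will be considered unacceptable". That would need two other DLTs as well as a discordant patient whose event is misattributed, and the same could be said of any misclassified event. It would also depend on which DLT definition governs. Section 12 requires a grade 3 or higher event that prevents completion of radiotherapy; section 13.5 also counts an M7824-related grade 3 or higher event that has not resolved to grade 1 or less within its stated period. Those two passages need reconciling in their own right. Section 12 limits adverse events to new or worsened conditions, and section 10.2 restricts when a laboratory abnormality is reported as one. The point does not rest on DLTs.
- A reader might also take section 2.5 to establish a liver signal. It names ALT increase among the event types in the 58 of 377 patients (15.4%) with a grade 3 or greater event, but gives no count for it. ALT increase is not in that section's list of most frequent treatment-related events.

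**Conclusion.** The point holds as a wording defect in an entry safeguard. As written, the transaminase line is met with one enzyme above 3 × ULN, and nothing else in the protocol numerically limits that enzyme. The limit should cover both enzymes, given the reported grade 3 or greater ALT increase and the baseline-dependent monitoring instruction in section 10.2.

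The effect is small. It is confined to patients with discordant enzymes who also satisfy the bilirubin limit and the hepatic exclusions. Their number is unknown and probably low. Sample size, power and the toxicity-monitoring operating characteristics do not change. It deserves correction at the next amendment but is no reason to question the design.

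The conclusion assumes that the line is applied as written and that the figure placed within the section 3.2 exclusion list, which was not readable, adds no enzyme limit.

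**What to change.** In section 3.1, reword the transaminase line so that AST *and* ALT *each* have to be at or below the limit already stated, 3 × ULN. The number does not change. Make the same edit in the eligibility checklist so that screening decisions follow one rule.

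The cost is a few words at the next amendment. A rare patient with one enzyme within the limit and the other above it would no longer qualify. If the sponsor did intend that one enzyme suffices, the protocol should say so explicitly and give the reason.
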